### 2.2 Secondary objective(s)

1. To evaluate the effect of sacubitril/valsartan vs. enalapril after 12 weeks of treatment on change from baseline in NT-proBNP.
2. To evaluate the effect of sacubitril/valsartan vs. enalapril after 12 weeks of treatment on the changes from baseline in echocardiographic measures including:
  - Global longitudinal strain
  - Left atrial volume index
  - Mitral annular E' velocity (Doppler Tissue Imaging)
  - Mitral E/E'
  - Left ventricular ejection fraction
  - Ventricular-vascular coupling (Ea/Ees)
  - LV end systolic and diastolic volume indices
3. To evaluate the effect of sacubitril/valsartan vs. enalapril after 4 weeks of treatment on the relation between the change in aortic characteristic impedance and change in biomarker levels, including BNP, U-cGMP/U-creatinine, during both trough and 4 hours post-dose.

### 3 Investigational plan

#### 3.1 Study design

This study will use a multicenter, randomized, double-blind, double-dummy, parallel group, active-controlled, forced titration, 12-week design in patients with heart failure and reduced left ventricular ejection fraction (LVEF)  $\leq 40\%$ . The study duration is a maximum of 30 weeks, including the screening epoch, with 8 scheduled outpatient visits.

##### Screening epoch

Patients will enter a screening epoch up to 6 weeks, beginning with Baseline (Visit 1) at - 42 to -1 day(s) prior to randomization to assess eligibility requirements and to confirm patients are on stable treatment with guideline-directed therapy for HFrEF, other than ACEis and ARBs.

- Screening/Baseline echocardiography (echo), ECG and safety labs will be obtained.
- Non-invasive arterial hemodynamics assessments will be obtained specifically within the window of study day -7 to -2 prior to randomization on Day 1 (Visit 2) to ensure quality control and to allow for a repeat study on day -1, if necessary.
- Biomarkers [REDACTED] will be obtained on Day 1 (Visit 2), pre-randomization.
- If the patient is currently taking an ACEi, a 36-hour washout is required prior to randomization (Visit 2).
- If the patient is currently taking an ARB, they must discontinue the ARB before initiation of study treatment however, washout is not required.

Note: Baseline for this study includes assessments performed during Screening and through Day 1 (Visit 2) pre-randomization.

Patients can be randomized as soon as screening criteria are met.

##### Double-blind, randomized treatment epoch

- On Day 1 (Visit 2), patients will be randomized to either sacubitril/valsartan 24/26 mg BID or enalapril 2.5 mg BID (Dose Level 1), according to the product label(s) and will return for a safety assessment at Week 1 (Visit 3).
- Study treatment will be force-titrated every 2 weeks to reach the target dose of sacubitril/valsartan 97/103 mg BID and enalapril 10 mg BID (Dose Level 3).

Deviation from the titration schedule or dose adjustments will only be allowed if indicated per protocol defined safety and tolerability criteria (See [Section 5.5.5](#), [Table 5-7](#)) and investigator judgement, if the investigator believes that adjustment/elimination of concomitant medications is not possible or does not alleviate the side effects of concern.

At any time during the 12 week randomized, double-blind treatment epoch, investigators have the option to withdraw patients from study treatment if they develop signs and symptoms of worsening heart failure for which the investigator would like to administer appropriate therapy. (See [Section 5.5.5](#) and [Section 5.5.6](#))

### Open-label extension epoch

The purpose of this open-label period is to observe the additional vascular effects of sacubitril/valsartan that occur beyond 12 weeks of treatment.

After 12 weeks of successful double-blind, active treatment, patients will continue into the 12 week open-label extension epoch. Patients will have received the final dose of double-blind treatment medication in the clinic at Week 12 (Visit 6).

- ALL patients will need to have a 36-hour washout from study treatment prior to starting the open-label extension to ensure that the blinding of the core study is maintained and to reduce the risk of angioedema.
- To facilitate this washout, patients will be instructed NOT to start their open-label treatment until the evening of the following day.
- All patients will start open-label treatment on sacubitril/valsartan 49/51 mg BID (Dose level 2), unless they completed the double-blind treatment epoch on Dose Level 1. Instead, these patients will enter the open-label epoch on sacubitril/valsartan 24/26 mg BID dose (Dose level 1).
- Study treatment will be force-titrated every 2 weeks to reach the target dose of sacubitril/valsartan 97/103 mg BID (Dose Level 3).

Deviation from the titration schedule or dose adjustments will only be allowed if indicated per protocol defined safety and tolerability criteria (See [Section 5.5.5](#), [Table 5-7](#)), and investigator judgement, if the investigator believes that adjustment/elimination of concomitant medications is not possible or does not alleviate the side effects of concern.

Follow-up safety visits will occur throughout the study at Weeks 1, 2, 4, 12, 14 and 24 (Visits 3, 4, 5, 6, 7, and 8).

Primary efficacy assessments will be conducted at Screening/Baseline, Day 1 (Visit 2) pre-randomization, and Week 12 (Visit 6).

[figure not shown]
Patients will be contacted by phone at approximately 30 days following the last administration of study treatment at Week 24 (Visit 8), or early withdrawal, in order to determine if any SAE(s) occurred during this time period. These SAEs will be recorded in the source document only and must be reported to Novartis. Attempts to contact the patient should also be recorded in the source document.

Every SAE occurring after the patient has provided informed consent and until 30 days following the last administration of study treatment must be reported directly to the Novartis Drug Safety and Epidemiology Department within 24 hours of learning of its occurrence.

No interim analysis is planned. If it is deemed necessary for internal decision making, due to patient safety, an interim analysis will be conducted by an independent statistical group.

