### **5.5.4 Instructions for prescribing and taking study treatment**

Novartis will supply the investigators with all medications sufficient for the course of the study. Patients will be provided with medication packs containing study drug corresponding to their assigned treatment arm and dose level, sufficient to last until the next scheduled visit. Patients will be instructed to hold their morning study medication dose on the day of study visits. Study drug will be administered at the site after pre-dose vital signs, blood samples and assessments are performed. Vital signs will include blood pressure, pulse and respiration measurements. BP will be measured using a standard sphygmomanometer with an appropriate sized cuff and the non-dominant arm in the seated position after 5 minutes of rest, with back supported and both feet placed flat on the floor. Every effort should be made to use the same arm for the patient for all vital signs assessments and where possible, the same person doing the assessment.

In order to adequately blind the study, patients will be required to take their assigned active treatment tablet along with placebo matching the opposite treatment twice daily. Patients will be instructed to take a total of two tablets by mouth twice a day for the duration of the double-blind treatment epoch, as follows:

- one tablet from the sacubitril/valsartan/sacubitril/valsartan matching placebo pack, and;
- one tablet from the enalapril/enalapril matching placebo pack

Table 5-5 summarizes the study drug that will be taken during the double-blind treatment epoch by visit and Table 5-6 summarizes the study drug that will be taken during the open-label treatment epoch.

Forced-titration will proceed according to the following table:

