- At Week 12 (Visit 6), patients will have the final dose of double-blind treatment medication administered in the clinic after pre-dose assessments have been completed. Drug accountability will be performed and all double-blind treatment medication will be returned to the site.
- All patients that complete the 12 week (Visit 6) double-blind treatment epoch will proceed into the 12-week open-label epoch on sacubitril/valsartan.
- Open-label sacubitril/valsartan will be dispensed at Week 12 (Visit 6) with patient instructions **NOT** to start their open label-treatment until the evening after completing a 36-hour wash out. All patients will have the wash out in order to maintain the blinding of the core study.

All dose levels will be available throughout the study. Dose adjustments to lower dose levels may be made at any time at both scheduled and unscheduled visits only if indicated for blood pressure control/tolerability reasons.

All study treatment assigned by the IRT will be recorded/databased in the IRT.

All dosages prescribed and dispensed to the patient and all dose changes during the study must be recorded in the IRT and on the Dosage Administration Record eCRF.

Study medication should be taken twice daily with a glass of water with or without food. Prior to scheduled study visit days, instruct the patient to have nothing by mouth after midnight and to take study medication after vital signs and study assessments are taken by the study coordinator at the investigator site.

If the patient misses taking any study drug dose, he/she should take it as soon as possible and within 4 hours of the scheduled dose time. If the patient is unable to take the missed dose within 4 hours of the scheduled dose time, he/she should skip the missed dose and return to his/her regular study drug administration schedule.

The investigator must promote compliance by instructing the patient to take the study treatment exactly as prescribed and by stating that compliance is necessary for the patient's safety and the validity of the study. The patient must also be instructed to contact the investigator if he/she is unable for any reason to take the study treatment as prescribed.

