**Table 5-9 Prohibited medication**

Medication	Prohibition period	Action taken
ACEis/ARBs/NEPs	ACEi 36 hour prior to study treatment, ACEi, ARB, NEP during study treatment, ACEi and NEP within 36 hours post double-blind randomization.	If the investigator believes that addition of an ACEi ARB or sacubitril/valsartan is necessary, then study drug must be discontinued, while monitoring renal function. ACEi or sacubitril/valsartan must not be started until 36 hours after discontinuing study drug to reduce the risk of angioedema.
Renin inhibitors (Aliskerin)	During study treatment.	Do not randomize, or, use alternate treatment.
Bile acid sequestering agents (such as cholestyramine or colestipol)	During study treatment.	Switch to alternate agent to avoid interference with study drug absorption. If use of alternate agent is not allowed, do not randomize or discontinue study drug treatment.
Nesiritide and intravenous nitrates	During study treatment.	Do not randomize. If hospitalized, either interrupt or discontinue study treatment. Nesiritide and intravenous nitrates have not been studied. Oral, topical and sublingual nitrates are permissible.

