4. Vital signs include blood pressure, pulse and respiratory rate measurements. BP will be measured using a standard sphygmomanometer with an appropriate sized cuff and the non-dominant arm in the sitting position after 5 minutes of rest, with back supported and both feet placed flat on the floor. Every effort should be made to use the same arm for the patient for all vital signs assessments and where possible, the same person doing the assessment.
5. A serum pregnancy test is not required for a woman who is sterile or who is post-menopausal. All serum pregnancy tests will be sent to the central laboratory.
6. Urine dipstick. If positive, send full urinalysis to central laboratory.
7. Clinical Chemistry: Repeat Full Chemistry Profile if Randomization (Visit 2) occurs greater than 2 weeks from Screening (Visit 1). Abbreviated Chemistry Panel (electrolytes and creatinine) is measured for safety at visits not requiring full chemistry profile. Hemoglobin A1c is measured at Screening and at Weeks 12 and 24 (Visits 6 and 8).
8. Must be strictly processed and stored according lab manual instructions and timelines.
9. Includes cardiac, renal, and drug mechanism of action biomarkers.
10. Includes urinary biomarkers such as U-cGMP/U-creatinine.
11. Echocardiography is completed simultaneously with hemodynamic assessments.
12. Screening echocardiography can be performed any time during the Screening/Baseline epoch, but should be performed before the hemodynamic assessment to ensure inclusion criterion is met first.
13. Fasting required after midnight prior to hemodynamics trough studies. Instruct and remind patient to take study medication the evening before the actual visit and no less than 12-hrs prior to the scheduled assessment time.
14. Screening hemodynamic assessment can be done within the window of day -7 to day -2 to allow sufficient time for a repeat test, if quality is not good.
15. Patient to remain at clinic for 4-hr post-dose hemodynamic assessment.
16. Instruct patient to take morning dose of study treatment in the clinic on the day of visit, after all pre-dose assessments have been completed.

Epoch		Screening/ Baseline**	Double-Blind Treatment					Open Label Treatment	Unsched. Visit o
Visit number	D/S*	1	2	3	4	5	6/EOT*	7	8/EOS**
Week		-6 to -1		1†	2	4	12	14	24

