Day		-42 to - 1	1	7	14	28	84	98	168

17. 36-hr washout required post-dose at Week 12 to avoid drug-drug interaction between ACEis and NEPi. Also, post-dose at Week 24 after open-label epoch is completed, if ACEi is to be initiated post-study.
 
18. Patients will be contacted by phone approximately 30 days following the last administration of study treatment (Week 24), or early study discontinuation, in order to determine if any SAE(s) occurred during this time period. Document in source. Every SAE occurring after the patient has provided informed consent and until 30 days following the last administration of study treatment must be reported to the Novartis Drug Safety and Epidemiology Department within 24 hours of learning of its occurrence.
 
19. Window for 4 hrs. post-dose assessments is <math>\pm</math> 0.5 hrs.
									

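### The open-label start instruction in Protocol section 3.1 carries no hour count, so it can give less than the 36-hour washout it is meant to deliver

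*Protocol*

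**What the plan says.** Protocol section 3.1 (Open-label extension epoch) places the last double-blind dose in the clinic at Week 12 (Visit 6). It then states the rule: "ALL patients will need to have a 36-hour washout from study treatment prior to starting the open-label extension". Its reasons are to protect the blind of the core study and to reduce the risk of angioedema. To bring the washout about, "patients will be instructed NOT to start their open-label treatment until the evening of the following day".

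Section 5.5.4, in the bullets after Table 5-5, words the start differently: patients are told not "to start their open label-treatment until the evening after completing a 36-hour wash out". Table 6-1, footnote 17, counts the interval from the dose: "36-hr washout required post-dose at Week 12 to avoid drug-drug interaction between ACEis and NEPi". Section 3.6.1 and SAP section 1.1 repeat the 36-hour requirement.

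On the timing of the Week 12 dose, section 5.5.4 says that "patients will have the final dose of double-blind treatment medication administered in the clinic after pre-dose assessments have been completed", and Table 6-1, footnote 16, gives the same order for visit days. Section 6.4.1 sets the trough study at about 08:00, permits 07:00 to 11:00, says that the study takes about an hour, and puts the 4-hour post-dose study at 12:00.

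**The concern.** The next evening is a calendar instruction, while the requirement is in hours. Whether one delivers the other depends on when the clinic dose was given and on what the patient takes evening to mean. The first varies by design and the second is undefined.

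The stake is safety. Section 3.6.1 says that angioedema risk rises when a patient takes both an ACE inhibitor and sacubitril/valsartan. Patients who had enalapril switch to sacubitril/valsartan at this point. Table 5-3 expects about 346 patients in the open-label epoch, so about 173 would come from enalapril if retention is equal in the two arms (an assumption). Under section 5.4, patients and site staff stay blinded until database lock, so nobody at the site can pick these patients out. One instruction has to be safe for everyone.

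For patients taken off study drug early, Table 5-9 states the same precaution in hours: "ACEi or sacubitril/valsartan must not be started until 36 hours after discontinuing study drug to reduce the risk of angioedema". The planned switch deserves the same precision.

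**Working it through.** **Inputs**
- Required washout: 36 h, counted from the Week 12 clinic dose (section 3.1; Table 6-1, footnote 17).
- Nominal dose time: 12:00 for the 4-hour study minus 4 h = 08:00 (section 6.4.1).
- Later dose times: the dose follows the pre-dose assessments, and the trough window runs to 11:00. A dose at 09:00 to 11:00 therefore fits the schedule even if the whole trough study must end by 11:00.
- Evening: not defined. **Assumption:** 20:00, with 18:00 to 23:00 as the range. For an 08:00 trough, section 6.4.1 requires the previous evening's dose at least 12 h before, so at or before 20:00. The central value is therefore plausible.

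**Formula.** With a dose at clock time t on the visit day and a start at clock time s on the next day:

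elapsed hours = 24 + (s − t)

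The 36 hours are met only if s ≥ t + 12.

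**The plan's own figure.** With t = 8 and s = 20, 24 + (20 − 8) = 36 h. The nominal schedule delivers exactly what the protocol requires, with no margin.

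**Over the permitted schedule** (hours from the clinic dose to a start on the next day):

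| Clinic dose | 36 h end next day at | Start 18:00 | Start 20:00 | Start 21:00 | Start 22:00 | Start 23:00 |
|---|---|---|---|---|---|---|
| 08:00 | 20:00 | 34 | 36 | 37 | 38 | 39 |
| 09:00 | 21:00 | 33 | 35 | 36 | 37 | 38 |
| 10:00 | 22:00 | 32 | 34 | 35 | 36 | 37 |
| 11:00 | 23:00 | 31 | 33 | 34 | 35 | 36 |

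At a 20:00 start, doses at 09:00 to 11:00 are 1 to 3 h short. At 18:00 even the 08:00 dose is 2 h short. At 23:00 every dose up to 11:00 complies.

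Section 6.4.1 does not say whether 11:00 limits the start or the end of the trough study. If it limits the start, a study of about an hour puts the dose at about 12:00, and a 20:00 start then gives 24 + (20 − 12) = 32 h.

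**The two sections compared.** After an 11:00 dose, section 3.1 read alone allows a start at 20:00 next day (33 h). Section 5.5.4 requires the 36 hours to be complete, so nothing before 23:00. A site that writes its patient instructions from section 3.1 alone could breach section 5.5.4.

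**The case against.** The strongest reply is that the protocol already controls this. The instruction in section 3.1 is introduced as the means to the washout, directly after the 36-hour rule and the statement that the last dose is given in clinic. A reader might infer that the start is not anchored to that dose at all; the text does not support this, because the following day can only mean the day after the clinic dose. What is missing is an hour count.

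A reader might also infer that sections 3.1 and 5.5.4 contradict each other. They do not. The instruction sets only an earliest time, and a site can satisfy both sections by following the stricter one. Nor is the rule waived: it appears in sections 3.1, 3.6.1 and 5.5.4, in Table 6-1 and in the SAP. Table 6-1 also has a washout row, marked at Visit 6 for entry in the clinical database.

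A further argument is that dosing is twice daily. If doses are about 12 h apart, skipping two and resuming with the third gives 36 h whatever the clinic dose time. That holds only if the patient's evening dose moves later along with a late clinic dose, and nothing in the instruction asks for this.

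What stands of the reply is that a short washout needs a late clinic dose, an evening start not moved to match, and reliance on section 3.1 without section 5.5.4 or the footnote. That limits the weight of the point. It does not make the instruction sufficient to deliver its own requirement.

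**Conclusion.** The point holds as a wording defect in a safety instruction. Section 3.1 implements a 36-hour rule with an instruction that is looser than section 5.5.4 and can miss the target within the protocol's own schedule. The size is 33 to 35 h for a 09:00 to 11:00 dose at an assumed 20:00 start, 31 to 38 h for those doses over starts from 18:00 to 23:00, and exactly 36 h for an 08:00 dose at 20:00.

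A reader might go on to infer that patients would be harmed, or that short washouts would be common. The documents support neither. They give no distribution of dose times, they do not include the patient-facing instruction sheets, and they do not quantify the excess angioedema risk of a washout a few hours short. The Week 12 primary endpoint is unaffected, because its assessments come before open-label dosing. The text should be corrected because the stake is safety and the correction is cheap; the 36-hour design itself is not in question.

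**What to change.** In both section 3.1 and section 5.5.4, replace the evening wording with: not before 36 hours after the Week 12 clinic dose, starting with the next scheduled dose (morning or evening) at or after that time. At Visit 6, write down each patient's earliest start date and time (clinic dose time plus 36 h).

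Section 5.5.4 has to change too. Its 36-hour condition is right, but it asks for an evening start. If the 36 hours end at 21:00 to 23:00, after a usual 20:00 dose time, a literal reading defers the start to 20:00 on the second day: 48 + (20 − 9) = 59 h after a 09:00 dose and 48 + (20 − 11) = 57 h after an 11:00 dose. Allowing a morning start avoids this.

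The cost is two wording changes and one recorded time per patient, with no extra visit. The downside is more time off drug for some patients. Those dosed at 09:00 to 11:00 who start at 08:00 on the second morning wait 48 + (8 − 9) = 47 h to 48 + (8 − 11) = 45 h, which is 9 to 11 h beyond the minimum and 12 h later than a 20:00 start. A patient dosed at 08:00 who starts at 20:00 sees no change.
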